### 5.2 Surgical Procedure

ALA will be mixed in the minimum volume of sterile water or juice immediately before use and given as a single bolus orally approximately 3 hours prior to scheduled anesthesia. Image-guided microsurgical resection of the tumor will be undertaken. Following the standard tumor resection under light microscopy, the residual tumor bed will be illuminated with blue light via a high pass optical filter in the microscopes light chain. The surgeon will examine the tumor bed with a barrier filter in the optical chain of the surgical microscope. The surgeon will quantitatively measure the concentration of Pp IX by placing the intraoperative fluorescence/reflectance probe in gentle contact with brain tissue by the surgeon for 3-5 seconds to make a recording. If fluorescence is present, and if safe, small biopsies will be taken from those areas of fluorescence as well as from non-fluorescing regions in the tumor resection cavity. When possible, the intent would be to collect a number of biopsies with a range of fluorescence intensities from each patient (at least one biopsy from normal-appearing tissues and at least one from the most fluorescent area). All biopsy specimens, including those taken from the bulk tumor, will be reviewed by a neuropathologist to assess tumor content. The expectation is that residual fluorescent tissue in the tumor cavity will be surgically removed (if deemed safe by the

neurosurgeon), potentially leading to more complete tumor resection. Pathologic confirmation of tumor type will be made by neuropathology.

Biopsies of fluorescent and non-fluorescent tissue within the tumor cavity will be graded by the surgeon at the time of biopsy as 0 to 3 fluorescence. A screen shot of the fluorescent image of the resected tumor illuminated with blue light via a high-pass filter will be documented for each patient with an integrating video camera. The fluorescence intensity and the quantitative measurement obtained with the intraoperative probe corresponding to each area on the screen shot from which biopsy is taken will be recorded by the surgeon in the operating room. The sample will be snap frozen in the operating room and provided to the pathologist for grading the tumor from 0 to 3 based on the degree of cellular infiltration. The scale to be used for grading is as follows:

Grade	Surgeon (intensity of fluorescence)	Pathologist (cell density)
0	No fluorescence	No tumor cell density content

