1	Mild brightness	Mildly infiltrating tumor cell density
2	Moderate brightness	Moderately infiltrating cell density
3	Intense brightness	Highly infiltrating cell density

The surgeon is responsible for:

- Identifying at least one fluorescent area within the tumor cavity and performing biopsy and grading that site's fluorescence.
- Identifying at least one non-fluorescent area within the tumor cavity and performing biopsy and grading that site's fluorescence.
- Labeling the areas (i.e. fluorescent or non-fluorescent) from which the biopsies are taken.

The pathologist is responsible for:

- Grading each frozen section biopsy for tumor content on a scale of 0 to 3.
- Labeling of specimens to be certain they correlate with biopsies taken by the surgeon.

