## **7 STATISTICAL CONSIDERATIONS**

### **7.1 Study Endpoints**

This is a single-center, single arm, open label phase II trial of fluorescence-guided resection by use of 5-aminolevulinic (ALA) at a dose of 20 mg/kg body weight in glioma patients. We hypothesize that surgical removal of the residual fluorescent tissues in the tumor cavity, presumably representing tumorous cells, will result in an increase in the amount of tumor removal during neurosurgical resection. In addition, we hypothesize that for recurrent malignant glioma, that the fluorescent material will reflect active viable tumor and not changes related to treatment such as macrophages or gliosis.

The primary analysis will be based on one biopsy taken from the most fluorescent area and one from normal appearing tissues for each patient as judged by the neurosurgeon.

The endpoints of interest in this study are as follows:

- Primary Endpoint: Positive Predictive Value (PPV), defined as the percentage of biopsies taken from the most fluorescent tissues determined by the pathologist as having tumorous content.
- Second Endpoints:
  - Negative Predictive Value (NPV), defined as the percentage of biopsies taken from non-fluorescent tissues determined as having no tumor content by the pathologist.
  - The safety of the use of 5-aminolevulinic (ALA) at a dose of 20 mg/kg body weight for neurosurgical resection in glioma patients
  - The correlation between fluorescent intensity as scored by the neurosurgeon and the tumor content as scored by the pathologist
  - The percentage of patients for whom there is no fluorescent tissue after surgery

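### The plan does not require the pathologist, whose grade decides PPV and NPV, to be masked to fluorescence status

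*Combined protocol and SAP*

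**What the plan says.** Section 7.1 defines PPV as the share of biopsies from the most fluorescent tissue that are "determined by the pathologist as having tumorous content". NPV is the mirror image in non-fluorescent tissue, and a further secondary endpoint correlates the surgeon's fluorescence score with the pathologist's tumor score. Section 7.2 calls the agent useful if at least 44 biopsies from the most fluorescent tissue, with 50 patients per subgroup, are read as containing tumor.

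Section 5.2 describes how specimens reach the pathologist:

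- Fluorescence intensity and probe value for each biopsied area are noted by the surgeon during the operation.
- The surgeon's duties include "Labeling the areas (i.e. fluorescent or non-fluorescent) from which the biopsies are taken".
- The pathologist's duties include "Labeling of specimens to be certain they correlate with biopsies taken by the surgeon".
- On the transfer itself, the plan says only this: "The sample will be snap frozen in the operating room and provided to the pathologist for grading the tumor from 0 to 3".
- The intent, where possible, is to take "a number of biopsies with a range of fluorescence intensities from each patient".

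Grade 0 on the pathologist's scale is no tumor cell content. Grade 1 is "Mildly infiltrating tumor cell density".

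No section mentions masking of the pathologist, coded specimens, an independent reader or a second reading.

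**The concern.** In diagnostic-accuracy terms, the surgeon's fluorescence call is the index test and the pathologist's grade is the reference standard. A reference standard read with the index result known can be pulled towards agreement with it. Here a specimen known to be fluorescent could move from grade 0 to grade 1 when the call is close, and one known to be non-fluorescent could move the other way. Both shifts favor the expected result, so PPV, NPV and the correlation could all be inflated.

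Two features of this trial make the point matter. It is single-arm and compares an absolute proportion with 80%, so no control group shares the reading error. And in the three recurrent subgroups the pathologist's call is itself the test of the hypothesis. Section 7.2 notes that treatment-related change is visible histologically after radiation and chemotherapy, and section 7.1 hypothesizes that "the fluorescent material will reflect active viable tumor and not changes related to treatment such as macrophages or gliosis". If the fluorescence result could influence that reading, the hypothesis would influence its own test.

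**Working it through.** **What the text allows.** Section 5.2 names one site label, fluorescent or non-fluorescent. It asks the pathologist to match specimens to the surgeon's biopsies and gives no neutral code for doing so. Several biopsies per patient imply some further identifier, but the plan does not say what it is or that it must be uninformative. A trial run exactly as written could therefore be graded masked or unmasked.

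**The plan's own figure.** Inputs from section 7.2: 50 patients per subgroup, null PPV 0.80, target PPV 0.92, success at 44 or more, one-sided exact binomial test.

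- P(Bin(50, 0.92) ≥ 44) = 0.898, which reproduces the stated power of about 90%.
- P(Bin(50, 0.80) ≥ 44) = 0.103, the chance of success at the null with no reading bias.

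**Illustration of unmasked reading.** Let p be the true PPV and u the share of tumor-free fluorescent biopsies called positive because their status is known. The values of u are assumptions; the plan has no source for them. The 75% row is also an assumed value. I take tumor content to mean grade 1 or higher, the natural reading of the scale, although section 7.1 does not map the endpoint to a grade.

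Apparent PPV = p + (1 − p)u

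Chance of success = P(Bin(50, apparent PPV) ≥ 44)

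For example, with p = 0.80 and u = 0.10, apparent PPV = 0.80 + 0.20 × 0.10 = 0.82, and the chance of success is 0.180.

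Each cell gives apparent PPV, then chance of success:

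| True PPV | u = 0 | u = 0.05 | u = 0.10 | u = 0.20 |
|---|---|---|---|---|
| 0.75 (assumed) | 0.7500; 1.9% | 0.7625; 3.1% | 0.7750; 4.7% | 0.8000; 10.3% |
| 0.80 (null) | 0.80; 10.3% | 0.81; 13.8% | 0.82; 18.0% | 0.84; 29.2% |
| 0.92 (target) | 0.920; 89.8% | 0.924; 91.7% | 0.928; 93.4% | 0.936; 96.1% |

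Expected changed calls per 50 = 50 × (1 − p) × u. At u = 0.20 this is 50 × 0.25 × 0.20 = 2.5 for p = 0.75, 50 × 0.20 × 0.20 = 2.0 for p = 0.80, and 50 × 0.08 × 0.20 = 0.8 for p = 0.92.

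**NPV.** The same algebra applies. If an assumed 10% to 20% of tumor-positive non-fluorescent biopsies were read as grade 0, an assumed true NPV of 0.50 would appear as 0.50 + 0.50 × 0.10 = 0.55 to 0.50 + 0.50 × 0.20 = 0.60.

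**The case against.** The strongest reply is that the plan never says the pathologist is unmasked. The surgeon's label is attached to areas of the cavity, not to specimen containers. Fluorescence and probe values are recorded by the surgeon in the operating room, and only the sample is said to go to the pathologist. The matching duty can be read as ordinary chain of identity. All of this stands, and it limits the finding to an omission. It does not supply the safeguard, because nothing in the text keeps the label from the reader.

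Other points stand in part:

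- The label is binary, so even if it reached the pathologist it would not show which fluorescent specimen was brightest or its 0 to 3 score. Inflation of the rank correlation is therefore less direct than inflation of PPV or NPV.
- The illustration lets errors run one way only, and the documents do not say how often a call is borderline.
- The illustration assumes 50 fluorescent biopsies per subgroup. Section 5.2 takes biopsies from fluorescent areas only where fluorescence is present and it is safe, and section 3.4 says visible detection in lower-grade glioma is limited. The percentages may not carry over to the two low-grade subgroups.
- The 10.3% at u = 0 is a property of the 44-of-50 rule and has nothing to do with masking.

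The open-label design is not an answer. It describes knowledge of treatment and does not prevent masked reading of specimens.

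**Conclusion.** The concern holds. The primary endpoint rests on a judgment between no tumor and mild infiltration, and the plan neither masks that judgment to the index-test result nor defines a specimen label that would make masking possible. Any bias would plausibly run towards success.

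Its size is unknown. Under the assumed values of u, the decision is most exposed near the 80% null, where an expected two changed calls in 50 would take the chance of a false success from 10.3% to 29.2%. It is least exposed at the 92% target. These figures depend on assumed upgrade rates, on error in one direction, and on 50 evaluable fluorescent biopsies. The plan should be changed on this point. Confidence is medium, because the documents do not show how specimens are actually labelled when they are read.

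**What to change.** Amend section 5.2 as follows:

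1. The surgeon labels specimens with neutral site codes, for example patient number plus A, B, C. Fluorescence status, surgeon grade and probe value stay on the operating-room record only.
2. The pathologist's second duty is reworded so that specimens are matched to the surgeon's biopsies by site code alone.
3. One sentence is added: the neuropathologist assigns the 0 to 3 study grade masked to fluorescence status, surgeon score and probe value, and codes are linked to the fluorescence data only after the grades are locked.

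The cost is low: a label convention, two edited bullets and one new sentence. Surgeon, pathologist, biopsies, patients, sample size and the 44-of-50 rule are unchanged. The downside is that someone must hold the code key, lock the grades and carry out the linking step at data entry. Grades already assigned with status known could be made masked only by re-reading.

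The remedy is partial. It removes expectation that comes from fluorescence status, but not expectation that comes from the known or presumed glioma diagnosis on which patients enter under section 4.1.

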### 5.3 Extent of Resection Follow-up

Patients will be assessed for completeness of tumor resection immediately following surgery (within 24 to 48 hours) using gadolinium enhanced brain MRI. Extent of resection will be assessed based on the finding of postoperative enhancement or lack of enhancement, on the postoperative imaging scans and will be evaluated as follows:

- Complete Resection (GTR): Resection of all enhancing disease
- Partial Resection (STR): At least a 50-90% decrease in the sum of the longest diameter (LD) of enhancing disease, taking as reference the baseline pre-operative MRI scan

- Near Complete Resection: Between a 90 and 99% resection of enhancing disease
- Minor Resection: All other situations (< 50% removal)

#### **5.4 Supportive Care**

Patients will be managed according to procedures for standard care established for postoperative brain resection patients. The patient will be kept in a "low light" environment for 72 hours following administration of ALA.

## **6 REGULATORY AND REPORTING REQUIREMENTS**

### **6.1 UCSF Data Safety Monitoring Plan for Phase II or III Institutional Study**

#### **Oversight and Monitoring Plan**

The UCSF-CCC Data Safety Monitoring Committee (DSMC) is responsible for monitoring data quality and patient safety for all UCSF-CCC institutional clinical studies. A summary of DSMC activities for this study includes:

- Review of subject data in each cohort
- Quarterly review for progress and safety
- Review of all serious adverse events
- Minimum of a yearly audit

### **6.2 Monitoring and Reporting Guidelines**

Investigators will conduct continuous review of data and patient safety at monthly study group or site committee meetings where the results of each patient's treatment are discussed and the discussion is documented in the minutes. The discussion will include the number of patients, significant toxicities as described in the protocol, doses adjustments, and observed responses. Quarterly summaries will be submitted to the DSMC for review. All grade 3-5 AE's and SAE's will be entered in the CCC Oncore database.

### **6.3 Review and Oversight Requirements**

#### **6.3.1 Adverse Event Monitoring**

Adverse Events (AEs) will be recorded on the Oncore database, all grade 3-5 expected and unexpected AEs will be recorded and updated at each visit.

##### **6.3.1.1 Serious Adverse Event Reporting**

Serious Adverse Event reporting will be in accordance with the UCSF- Committee on Human Research Regulations and Code of Federal Regulation Title 21 Volume 5 Part 312.32.

UCSF CHR website for guidance in reporting serious adverse events  
[http://www.research.ucsf.edu/chr/Guide/Adverse\\_Events\\_Guidelines.pdf](http://www.research.ucsf.edu/chr/Guide/Adverse_Events_Guidelines.pdf)

FDA website for guidance in reporting serious adverse events  
<http://www.accessdata.fda.gov/scripts/cdrh/cfdocs/cfcfr/CFRSearch.cfm?fr=312.32>

MedWatch forms and information:  
<http://www.fda.gov/medwatch/getforms.htm>

Serious Adverse events will be reported on the MedWatch form. A copy of the MedWatch report and CHR forms must be sent to CCC- DSMC at Box 1297. The date the SAE was sent to all required reporting agencies will be documented and one Oncore, hard copies of the report will be maintained in the regulatory files.

**If the SAE is death and determined to be possibly, probably or definitely related to the investigational drug or any research related procedure, the event must be reported to the DSMC Chair or his designee within 24 business hours. The reporting procedure is by personal communication via phone or in person with written documentation of the 1:1 communication via e-mail with a copy of the e-mail to DSMC Administrator and DSMC Coordinator.**

### **6.3.2 Review of Adverse Event Rates**

If the study has an increase of unexpected or expected Adverse Events, grade 3 or 4 above the rate reported in the Investigational Brochure or package insert, the increase rate of AEs will be reported to the DSMC at the time of Identification. The Chair and PI will discuss the finding and proceed with a written course of action. Each quarterly report will indicate if the AE incidence is within the scope of the investigational brochure or package insert. If at any time the Investigator stops enrollment or stops the study due to safety issues, the DSMC Chair and Administrator must be notified within 24 business hours via e-mail. The DSMC must receive a formal letter within 10 business days and the CHR must be notified.

### **6.3.3 Study Progress – Quarterly Review**

Principal Investigators are required to submit quarterly study progress reports to determine whether accrual projections are being met, to summarize grade 3 and 4 toxicities (expected and unexpected) and SAE reports. This report will also indicate if the rate of all grade

3-5 AE's are above the AE rates documented in the Investigational Brochure or package insert. In addition, a progress report on recruitment and subjects known responses to the investigational therapy must be submitted. At this time also send the committee all external DSMB reports and formal audit reports.

These quarterly reports are reviewed at Data Safety Monitoring Committee meetings. These reports are required: February 1, May 1, August 1, and October 1. Failure to submit such reports may result in trial suspension. Send reports to: DSMC Box 1297

Data Safety Monitoring Committee Contacts:

DSMC Chair: [name]

[contact]

Email [contact]

Box 1705

#### 6.4 Adverse Event Reporting

An adverse event is any untoward medical occurrence in a patient administered a pharmaceutical product, which does not necessarily have a causal relationship with the treatment. An adverse event can be any unfavorable and unintended sign (e.g. including an abnormal laboratory finding), symptom, or disease temporally associated with the use of the drug, whether or not it is considered to be drug related. This includes any newly occurring event or previous condition that has increased in severity or frequency since the administration of the drug.

A serious adverse event (SAE) is any adverse event, occurring at any dose and regardless of causality that:

- is fatal
- life-threatening Life -threatening means that the patient was at immediate risk of death from a reaction as it occurred (i.e., does not include a reaction which hypothetically might have caused death had it occurred)
- requires inpatient hospitalization or prolongation of existing hospitalization
- results in persistent or significant disability/incapacity
- is a congenital anomaly/birth defect
- is an important medical event, which is defined as an event that may not result in death, be life-threatening, or require hospitalization but may be considered an SAE when, based upon appropriate medical judgment, it may jeopardize the patient and may require medical or surgical intervention to prevent a SAE.

Since potential adverse events related to ALA are known to be transient in nature, it is felt that a 14-day evaluation window is relevant to assess the safety profile of this agent. All adverse events will be collected from the time of drug administration and will continue to be collected until 14 days (+/- 3days) from the time of drug dosing. In addition, serious adverse events (SAE) will be collected beginning from the time the subject signs the informed consent.

The descriptions and grading scales found in NCI Common Terminology Criteria for adverse events (CTCAE) version 3.0 will be utilized for adverse event reporting and are available on line <http://ctep.cancer.gov/reporting/ctc.html>. SAEs and expedited reporting of specific expected AEs will be submitted to the FDA via the FDA safety information and adverse event reporting system MedWatch, FDA form 3500A.

#### **6.4.1 Probable ALA adverse events to be expected**

Transient side effects have been noted, most commonly, skin photosensitivity, nausea, vomiting, abdominal discomfort, and lowering of blood pressure which can result in lightheadedness. Since ALA may cause nausea and vomiting, patients will be monitored and treated as needed with anti-nausea medication.

Dose-dependent abnormalities in liver function tests have been documented. The most common effect has been a rise in transaminases (typically AST), (23-29). Liver function tests AST and ALT will be performed throughout the study, please see the Study calendar provided in section 4.4.

ALA-induced Pp IX accumulation occurs predominantly in cells of epithelial origin and isolated cases of skin photosensitivity with subsequent cutaneous injury after sun/bright light exposure have been reported (29, 30). Skin reactions in clinical photodynamic therapy trials with doses of 30-60 mg/kg have been mild, consisting primarily of erythema that resolved within 24 to 48 hours. Blister formation and/or skin necrosis have not been reported in these trials and neither have any indications of ocular sensitivity been described with systemic ALA. Precautions will be taken to protect the patient from the effects of skin photosensitivity during surgery. Patients will receive instructions on how to protect themselves and to minimize exposure to sunlight and/or indoor lighting for up to 72 hours. Patients with a history of cutaneous photosensitivity, porphyria, hypersensitivity to porphyrins, photodermatitis, exfoliative dermatitis or an inability to comply with the photosensitivity precautions associated with the study will be excluded from enrollment.

The light dose (due to fluorescence excitation) to the brain during fluorescence image-guided resection can be estimated to be approximately  $216 \text{ J.cm}^{-2}$ , based on data presented in Stummer (11), an irradiance of  $\sim 60 \text{ mW.cm}^{-2}$ , and an approximate illumination time of 1 hour. The risk of complications due to a potential PDT effect are considered minimal since no serious adverse events were reported by Stummer (11, 14), the ALA dose in our trial (20 mg/kg) is equal to that used in these studies and is lower than the ALA doses used for PDT which typically reach 60mg/kg (12, 23-28, 30-38).

#### **6.4.2 Other possible adverse events**

The following more serious expected adverse events that could occur in this study protocol will not require expedited reporting, but the event will be captured in the patient's study file.

- Reaction to anesthesia.
- Balance problem as the results of the tumor itself or from the surgery to correct it.

- Bleeding which may occur as the result of the surgery or from medications.
- Blood clot development, which may occur with any surgery.
- Brain injury that could happen depending on the location of the tumor and removal procedure.
- Cardiac complications since there is a chance the procedure could cause an irregular heartbeat or heart attack.
- Functional loss as there is a possibility of experiencing problems such as opening the mouth, chewing, speech, language, and memory difficulties following surgery.
- Hydrocephalus as it is possible that the normal flow of spinal fluid around the brain may be altered.
- Infection that may occur at the incision site and may also occur within the bone flap. Infection-related risks also include meningitis or a brain abscess.
- Loss of nerve function or paralysis.
- Post-operative pain such as a headache that may persist for a week to a month and sometimes for a longer time period.
- Recurrence of the tumor may return to the same site.
- Respiratory difficulties, which could include breathing difficulties, post-operative pneumonia or a pulmonary embolus.
- Seizure activity.
- Visual disturbance.

